2.2.3.3. Combination of JNJ-3989 and PegIFN- $\alpha 2a$

PegIFN- $\alpha 2a$ is a covalent conjugate of recombinant alfa-2a interferon that is indicated for the treatment of chronic HBV infection in adult and pediatric patients at least 3 years of age. In addition, PegIFN- $\alpha 2a$ in combination with other medicinal products is indicated for the treatment of chronic hepatitis C virus (HCV)-infection in adult and pediatric patients at least 5 years of age and not treated before. The most common adverse reactions ($\geq 10\%$ of participants) are anorexia, anxiety, headache, concentration impairment, dyspnea, cough, alopecia, dermatitis, pruritis, dry skin, myalgia, arthralgia, asthenia, pyrexia, and fatigue. For further information regarding PegIFN- $\alpha 2a$, refer to the currently approved prescribing information.

Treatment with PegIFN- $\alpha 2a$ has been associated with decreases in platelet count (common adverse reaction). Of the 84 adult chronic HBV-infected participants that received 3 subcutaneous injections of JNJ-3989 in the Phase 1/2a AROHBV1001 study (see Section 2.2.3.1, JNJ-3989), 6 participants developed Grade 1 platelet reduction with no general trend towards a continuous decline.

No pharmacokinetic (PK) interaction is expected between JNJ-3989 and PegIFN- $\alpha 2a$ based on the known pharmacologic profile of JNJ-3989 (IB JNJ-3989; Yeh 2019).

At the time of protocol writing, 2 clinical studies using the combination of JNJ-3989 and PegIFN- α 2a are ongoing: REEF-IT and PENGUIN. Nonclinical studies to investigate the effect on platelet count decreases were completed and results are summarized in Section 2.2.2.1, JNJ-3989. Up to 48-week hematology data from the ongoing Phase 2 clinical study REEF-1 are available and overall around 5% of the participants experienced AEs or laboratory abnormalities related to hematologic abnormalities, the majority of mild to moderate severity. The hematologic abnormalities resolved on continued JNJ-3989+NA treatment.

2.3. Benefit-Risk Assessment

More detailed information about the known and expected benefits and risks of JNJ-3989 may be found in the IB ([IB JNJ-3989](#)).

For the benefit-risk evaluation of ETV, tenofovir disoproxil, TAF, and PegIFN- α 2a, refer to the respective prescribing information and Summary of Product Characteristics.

2.3.1. Benefits for Study Participation

2.3.1.1. Known Benefits

The clinical benefit of JNJ-3989 remains to be established.

2.3.1.2. Potential Benefits

Results from clinical studies with JNJ-3989, NAs, and PegIFN- α 2a may be useful for the development of a novel therapeutic approach for chronic HBV infection.

JNJ-3989 on a background of NAs would target different stages of the viral life cycle. While NA treatment reduces HBV DNA to levels close to or below the lower limit of quantification (LLOQ) of the HBV DNA assay, HBV replication is not completely inhibited, resulting in replenishment of the cccDNA pool. The addition of JNJ-3989 is expected to intensify viral suppression by downregulating levels of the HBV DNA precursor pgRNA. In addition, JNJ-3989 reduces levels of all viral proteins including HBsAg, which is known to interfere with the host immune responses ([Fang 2015](#); [Li 2018](#); [Wang 2013](#)). By acting on both viral replication and by reducing barriers to the host immune-responses, higher functional cure rates may be achieved.

The addition of PegIFN- α 2a (12 or 24 weeks, with immediate or delayed start) to the regimen may lead to further improvement of the immune response (such as reactivation of NK-cells) and ultimately could lead to immune control of HBV (ie, functional cure). In addition, PegIFN- α 2a has shown to have direct antiviral effects on HBV which could also contribute to the efficacy of the regimen. By adding PegIFN- α 2a to the regimen, higher functional cure rates may be achieved.

2.3.2. Risks for Study Participation

2.3.2.1. Known Risks

Injection site reactions were the most frequently observed AEs assessed as related to JNJ-3989 by the investigator.

The side effect profile of PegIFN- α 2a is well established and includes, but is not limited to, neuropsychiatric, autoimmune, ischemic, ophthalmologic, hematological, and infectious disorders. Exacerbations of hepatitis during hepatitis B therapy are common and characterized by transient and potentially severe increases in serum ALT. Marked increases in ALT were sometimes accompanied by bilirubin elevation and other liver test abnormalities. In many, but not all cases, these disorders resolve after stopping PegIFN- α 2a therapy. For a full list of known risks for PegIFN- α 2a, refer to the respective prescribing information and Summary of Product Characteristics.

2.3.2.2. Potential Risks

All therapies have the potential to cause adverse experiences. In addition, the discontinuation of NA treatment bares a risk of hepatitis B flares.

Please refer to Section 2.2, Background, for details on the safety results in the studies conducted to date.

2.3.2.2.1. Potential Risks for JNJ-3989

ALT Elevations:

ALT elevation is considered an important potential risk for JNJ-3989. Two distinct patterns of ALT elevations have been observed: a rapidly rising and resolving ALT elevation, or a sustained pattern of ALT elevation. In a Phase 2 study involving chronic HBV-infected participants (REEF-1), ALT flares (ALT ≥ 3 x ULN and ≥ 3 x Nadir) were observed in 7% of participants treated with 200 mg JNJ-3989 every 4 weeks, compared to 0% of participants treated with NA and 0% to 2% of participants treated with lower doses of JNJ-3989. The majority of the ALT flares resolved rapidly on continued treatment; 1 was considered serious. In REEF-D, an ongoing study with HBV/HDV co-infected participants, 10 out of 22 (45%) participants have developed ALT elevations. Study treatment assignment remains blinded. Three participants have experienced prolonged elevation of ALT. In 2 participants the ALT elevation was considered serious. ALT elevation has led to discontinuation of blinded study treatment in 2 participants. A causal association of ALT elevations with JNJ-3989 has not been confirmed and the underlying mechanism for ALT elevations being more frequent in context of HBV HDV co-infection is not yet understood.

Reproductive Risks and Pregnancy

In the EFD studies, JNJ-3989 was not teratogenic in rats and rabbits. The fertility in male and female rats is not impacted with JNJ-3989 up to a dose of 180 mg/kg/week.

Based on the difference in metabolic pathways and in vitro data indicating absence of impact of JNJ-3989 on cytochrome P450 [CYP] enzymes and transporters, no clinically relevant interactions are anticipated between JNJ-3989 and oral contraceptives.

Potential Genotoxicity

JNJ-3989 is considered to be devoid of genotoxic activity. Nonclinical carcinogenicity studies have not been conducted.

Other Potential Toxicity/Events of Special Interest

JNJ-3989 is considered non-cytotoxic, did not activate human platelet aggregation, did not activate the innate immune system to a significant degree in vitro, and did not activate complement in vitro.

Viral Resistance

Treatment with JNJ-3989 may lead to viral resistance, but resistance to JNJ-3989 is not anticipated to impact treatment with other siRNAs, unless they would have an overlapping trigger binding region. Note that none of the siRNAs in development have overlapping regions. Using these agents in combination, especially in combination with ETV or tenofovir, is expected to minimize the risk of emerging resistant viral variants.

2.3.2.2.2. Potential Risks for Entecavir, Tenofovir Disoproxil, Tenofovir Alafenamide, and PegIFN- α 2a

For the general potential risks of ETV, tenofovir disoproxil, TAF, and PegIFN- α 2a, refer to the respective prescribing information and Summary of Product Characteristics.

Risks specific for this study design are listed below:

- PegIFN- α 2a might increase the immunogenicity of JNJ-3989.
- Combination of PegIFN- α 2a and JNJ-3989 might increase the risk of hematologic abnormalities and/or of bone marrow suppression.

2.3.3. Benefit-Risk Assessment for Study Participation

Based on the available data and proposed safety measures, the overall risk/benefit assessment for JNJ-3989 clinical studies is deemed acceptable for the following reasons:

- JNJ-3989 was generally safe and well tolerated during the Phase 1/2a Study AROHBV1001 (see Section 2.2.3.1, JNJ-3989). All but one AE were mild or moderate in severity. All ISRs, identified as adverse drug reactions for JNJ-3989, were mild in intensity.
- Based on pre-clinical and clinical data available today, the combination of JNJ-3989, NA (ETV, tenofovir disoproxil, or TAF), and PegIFN- α 2a is considered safe. Data from nonclinical combination toxicity studies (Section 2.2.2.3, Combination of JNJ-3989 and PegIFN- α 2a) confirmed that combination of PegIFN- α 2a with JNJ-3989 did not induce any synergistic or additive effect in monkeys up to 3 months of treatment. Forty-eight (48)-week hematology data of ongoing Phase 2 clinical study REEF-1 (Section 2.2.3.3, Combination of JNJ-3989 and PegIFN- α 2a) has been reviewed and no safety concern has been identified.
- Events of Special Interest are significant AEs that are judged to be of special interest because of clinical importance, known class effects or based on nonclinical signals. Events of Special Interest for JNJ-3989 that will be carefully monitored during the study include ISRs, ALT/AST elevations, and hematologic abnormalities (see Section 8.3.6, Adverse Events of

Special Interest). In addition, the following toxicities will also be carefully monitored: rash, renal complications, and acute systemic allergic reactions (Section 8.3.7, Other Toxicities).

- Continued careful assessment of the safety, efficacy, and PK during treatment is included in this study.
- To minimize potential risk and stress to participants, the following measures are in place:

Utilization of selection criteria which exclude participants who may potentially be at higher risk of an AE (see Section 5, Study Population).

Utilization of withdrawal criteria (see Section 7, Discontinuation of Study Intervention and Participant Discontinuation/Withdrawal). If a participant drops out due to withdrawal of consent, he/she retains the option to participate in the safety follow-up procedures.

At regular time points throughout the study (see [Schedule of Activities](#)), blood samples for biochemistry, blood coagulation, and hematology and urine samples for urinalysis, urine chemistry, and renal biomarkers will be collected. Vital signs (systolic and diastolic blood pressure, pulse rate, and body temperature), height (only at screening), body weight, and electrocardiograms (ECGs) will be recorded throughout the study. Physical and ophthalmologic examinations will be performed and AEs will be assessed (see Section 8.2, Safety Assessments). Events of Special Interest will be closely monitored (Section 8.3.6, Adverse Events of Special Interest).

The impact of PegIFN- α 2a addition to JNJ-3989 on ALT elevations is not known in context of HBV monoinfection. Strict rules for management of ALT elevation are in place (refer to Section 8.3.6.2, Intervention-emergent ALT/AST Elevations).

An internal Data Review Committee (DRC) will be established for continuous monitoring of SAEs, AEs leading to discontinuation, and ALT flares to ensure the continuing safety of the participants enrolled in the current study. In addition, an Independent Flare Expert Panel (IFLEP) will be appointed to characterize and adjudicate each ALT flare. See Section 10.3.6, Committees Structure.

Participants will be monitored closely during the 48-week FU Period, with frequent follow-up visits. Participants who completed NA treatment after meeting the NA treatment completion criteria (Section 6.5.1, NA Treatment Completion) based on the Week 24 (EOSI) or FU Week 2 results, should re-start NA treatment if pre-defined NA re-treatment criteria are met (Section 6.5.2, NA Re-treatment Criteria During Follow-up).

JNJ-3989 will be administered using a proper subcutaneous technique to decrease the risk of ISRs. ISRs will be managed as outlined in Section 8.3.6, Adverse Events of Special Interest.

Any clinically significant abnormalities persisting at the end of the study/early discontinuation will be followed up by the investigator until resolution (return to baseline) or until stabilization (to be agreed upon with the Sponsor).

3. OBJECTIVES AND ENDPOINTS

Below is the list of objectives and endpoints that will be evaluated in this study, delineating the details in alignment with the general objectives listed in the Master Protocol PLATFORMPAHPB2001. The details specific for this ISA are highlighted (colored fill).

Objectives	Endpoints
Primary	

 To evaluate the efficacy in terms of HBsAg changes from baseline for the treatment regimens of 24 weeks of JNJ-3989 + 24 weeks of NA + 12 or 24 weeks of PegIFN-α2a (with immediate or delayed start of PegIFN-α2a treatment), as compared to NA standard of care treatment. 	
 Proportion of participants with a reduction of at least 2 log₁₀ IU/mL in HBsAg levels from baseline at Week 24 (EOSI).
Secondary	

 To evaluate the safety and tolerability of the study intervention. 	
 Safety and tolerability including but not limited to the proportion of participants with (S)AEs and abnormalities in clinical laboratory tests (including hematology, blood biochemistry, blood coagulation, urinalysis, urine chemistry, renal biomarkers), 12-lead ECGs, vital signs, and ophthalmologic and physical examinations throughout the study.

 To evaluate the efficacy of the study intervention at the end of the 24-week treatment period. 	
 Proportion of participants meeting the protocol-defined NA treatment completion criteria based on the Week 24 (EOSI) or FU Week 2 results.

 To evaluate the efficacy of the study intervention during the FU period in those participants who met the protocol-defined NA treatment completion criteria based on the Week 24 or FU Week 2 results. 	
 Proportion of participants with HBsAg seroclearance at FU Week 24 and 48 (ie, 24 and 48 weeks after completion of all study interventions at Week 24) without re-starting NA treatment. Proportion of participants with HBV DNA <LLOQ at FU Week 24 and 48 (ie, 24 and 48 weeks after completion of all study interventions at Week 24) without re-starting NA treatment. Frequency of virologic and/or biochemical flares. Proportion of participants requiring NA re-treatment.

 To evaluate the efficacy of the study intervention as measured by blood markers (such as HBsAg, HBeAg, HBV DNA, and ALT) during the study intervention and follow-up (FU) period. 	
 Proportion of participants with HBsAg, HBeAg, HBV DNA, and ALT levels below/above different cut-offs over time. Proportion of participants with HBsAg seroconversion. Change from baseline over time in HBsAg. Time to achieve HBsAg seroclearance/seroconversion, and/or HBV DNA <LLOQ.

Objectives	Endpoints

 To evaluate the frequency of virologic breakthrough throughout the study. 	
 Proportion of participants with virologic breakthrough^a.

 To evaluate the PK of JNJ-3989 (JNJ-3924 and JNJ-3976), and optionally of NA and PegIFN-α2a. 	
 PK parameters of JNJ-3989 (JNJ-3924 and JNJ-3976). Optionally, PK parameters of NA and/or PegIFN-α2a.
Exploratory	

 To explore host and viral baseline and on-treatment markers associated with end of study intervention and/or off-treatment response. 	
 Association of baseline characteristics and baseline/on-treatment viral and host blood markers with selected on or off-treatment efficacy variables.

 To explore changes in the severity of liver disease. 	
 Changes in fibrosis (according to Fibroscan liver stiffness measurements) at EOSI and the end of the FU period versus baseline.

 To explore efficacy of the study intervention in terms of changes in HBV RNA and hepatitis B core-related antigen (HBcrAg) levels during the study intervention and FU period. 	
 Changes from baseline in HBV RNA and HBcrAg levels over time.

 To explore the relationship of PK with selected pharmacodynamic (PD) parameters of efficacy and safety. 	
 Relationship of various PK parameters with selected efficacy and safety endpoints.

 To explore the HBV genome sequence during the study intervention and FU period. 	
 Assessment of intervention-associated mutations over time.

 To explore HBV-specific T-cell responses during the study intervention and FU period.^b 	
 Changes from baseline in HBV-specific peripheral blood T-cell responses over time.^b

 To explore the efficacy of NA re-treatment in participants who meet the criteria for NA re-treatment. 	
 Proportion of participants who reach HBV DNA <LLOQ after re-start of NA treatment during the FU period.

 To explore medical resource utilization (MRU) to manage participants during study intervention and follow-up. 	
 Number and duration of medical care encounters, including surgeries, and other selected procedures (inpatient and outpatient) Duration of hospitalization (total days length of stay, including duration by wards; eg, intensive care unit) Number and character of diagnostic and therapeutic tests and procedures Outpatient medical encounters and treatments (including physician or emergency room visits, tests and procedures, and medications)

^a For the definition of virologic breakthrough, refer to Section 10.1, Appendix 1: Abbreviations and Definitions.

^b Peripheral blood mononuclear cell (PBMC) samples for immune analyses will be collected at selected sites only.

Refer to Section 8, Study Assessments and Procedures for evaluations related to endpoints.

For the definitions of terms, refer to Section 10.1, Appendix 1: Abbreviations and Definitions.

HYPOTHESIS

The primary hypothesis of this study is that at least one of the combination regimens of JNJ-3989+NA+PegIFN- α 2a is more efficacious than NA treatment alone (standard of care), as measured by the primary efficacy endpoint, the proportion of participants with a reduction of at least 2 log₁₀ IU/mL in HBsAg levels from baseline at Week 24. Because the study does not include a control arm, the hypothesis is formulated assuming a fixed external NA control response rate of 2% in terms of the primary efficacy endpoint.

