All participants will receive the last dose of JNJ-3989 at Week 24 and the last dose of PegIFN- α 2a at Week 23 (Arms 1 and 2) or Week 11 (Arm 3). They will start the FU Period after the Week 24 visit. If the protocol-defined NA treatment completion criteria (see Section 6.5.1, NA Treatment Completion, for more details) are met based on the Week 24 results, NA will be stopped at the next scheduled visit (ie, FU Week 2), otherwise NA treatment will continue during the complete FU Period. **Note:** Participants who are close to meeting the protocol-defined NA treatment completion criteria with the Week 24 results, and do meet the criteria based on the FU Week 2 results may be allowed to stop NA at FU Week 4, after consultation with the Sponsor.

Participants who meet the protocol-defined NA treatment completion criteria will be monitored closely during the 48-week FU Period with a study visit at least once every 4 weeks. NA treatment should be re-started in accordance with the NA re-treatment criteria (see Section 6.5.2, NA Re-treatment Criteria During Follow-up, for more details).

Study intervention consists of:

- JNJ-3989: 200 mg subcutaneous injection Q4W
- NA: tenofovir disoproxil (245 mg), or TAF (25 mg), or ETV (0.5 mg) tablets p.o. QD
- PegIFN- α 2a: 180 μ g subcutaneous injection QW.

Both the Platform Master informed consent form (ICF) and the ISA ICF must be signed before the first study-related activity takes place.

Assessments and sampling include:

- Safety and tolerability, based on AEs, laboratory assessments, ECGs, vital signs, ophthalmologic and physical examination, will be assessed throughout the study from the time that the ISA ICF is signed until the completion of the last study-related activity (see Section 8.2, Safety Assessments, and Section 8.3, Adverse Events and Serious Adverse Events).
- Efficacy will be evaluated using different parameters including HBsAg, HBeAg, and HBV DNA (see Section 8.1, Efficacy Assessments).
- Samples for HBV genome sequencing will be taken at the time points indicated in the [Schedule of Activities](#) (see Section 8.1.1, Sequencing). Samples may be sequenced based on the Sponsor virologist's request, considering the HBV DNA levels. In case of a virologic breakthrough/flare, additional samples for viral sequencing may be taken.

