6.5.1. NA Treatment Completion

All participants will receive the last dose of JNJ-3989 at Week 24 and the last dose of PegIFN- α 2a at Week 23 (Arms 1 and 2) or Week 11 (Arm 3). They will start the FU Period after the Week 24 visit. If all of the following NA treatment completion criteria are met based on the Week 24 results, treatment with NA will be stopped at the next scheduled visit (ie, FU Week 2):

- The participant has ALT <3x ULN, AND
- The participant has HBV DNA <60 IU/mL at Week 24 and HBV DNA <LLOQ at the previous visit, or HBV DNA <LLOQ at Week 24, AND
- The participant is HBeAg-negative, AND
- The participant has HBsAg <100 IU/mL.

Note: Participants who are close to meeting the protocol-defined NA treatment completion criteria with the Week 24 results, and do meet the criteria based on the FU Week 2 results may be allowed to stop NA at FU Week 4, after consultation with the Sponsor. In case of ALT elevation \geq 3x ULN at Week 24, the investigator must consider different potential causes of increased ALT to ensure appropriate work up and management as needed. If the ALT elevation is unrelated to HBV activity and/or <3x ULN by FU Week 2, NA completion may be considered at the discretion of the investigator and in consultation with the sponsor.

Participants who do not meet the above criteria based on the Week 24 or FU Week 2 results should continue NA treatment during the 48-week FU Period.

Participants who meet the above-mentioned NA treatment completion criteria will be monitored closely during the 48-week FU Period with a study visit at least once every 4 weeks. NA treatment should be re-started in accordance with the NA re-treatment criteria (see Section [6.5.2](#), NA Re-treatment Criteria During Follow-up, for more details).

The investigator should consider to re-start NA treatment per local standard of care at the EOS visit (Follow-up Week 48) for participants who met the NA treatment completion criteria based on the Week 24 (or FU Week 2) results, who did not re-start NA treatment during the follow-up phase, and who did not achieve and maintain HBsAg seroclearance. NA will not be provided by the sponsor after the final study visit.

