ISR	injection site reaction
KPD	kinetic pharmacodynamic model
LLN	lower limit of normal
LLOQ	lower limit of quantification
MDSC	myeloid-derived suppressor cell
MoA	mode of action
MRI	magnetic resonance imaging
MRU	medical resource utilization
NA	nucleos(t)ide analog
NIMP	non-investigational medicinal product
NK	natural killer
NOAEL	no observed adverse effect level
PBMC	peripheral blood mononuclear cell
PD	pharmacodynamic(s)
PegIFN- α 2a	pegylated interferon alpha-2a
pgRNA	pre-genomic ribonucleic acid
PK	pharmacokinetic(s)
PoC	proof of concept
Q4W	every 4 weeks
QW	weekly
QD	once daily
QTcF	QT interval corrected for heart rate according to Fridericia's formula
RBC	red blood cell
rcDNA	relaxed circular deoxyribonucleic acid
RNAi	ribonucleic acid interference
SAE	serious adverse event
SAP	Statistical Analysis Plan
SD	standard deviation
SDM	site-directed mutant
SE	standard error
siRNA	small interfering ribonucleic acid
$t_{1/2\text{term}}$	terminal half-life
T4	thyroxine
TAF	tenofovir alafenamide
TEAE	treatment-emergent adverse event
t_{max}	time to reach C_{max}
TND	target not detected
TNF	tumor necrosis factor
TSH	thyroid stimulating hormone
WBC	white blood cell

Definitions of Terms

ALT/AST nadir	Lowest ALT/AST value during study participation
End of study intervention (EOSI)	Time of the last administration of study intervention
Functional cure (FC)	HBsAg seroclearance at 24-weeks after EOSI
HBsAg or HBeAg seroclearance	HBsAg or HBeAg negativity, respectively, based on the assay used
HBsAg or HBeAg seroconversion	HBsAg or HBeAg negativity and anti-HBs or anti-HBe antibody positivity, respectively
IC ₅₀	half maximal inhibitory concentration
Study intervention	JNJ-73763989 (JNJ-3989), NA (either ETV, tenofovir disoproxil, or TAF), and PegIFN- α 2a
Virologic breakthrough	Confirmed on-treatment HBV DNA increase by $>1 \log_{10}$ IU/mL from nadir or confirmed on-treatment HBV DNA level >200 IU/mL in participants who had HBV DNA level $<$ LLOQ of the HBV DNA assay.

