##### **5.4.1.1.4.2. Off Treatment**

HBsAg seroclearance will be evaluated over time at each of the FU timepoints separately, with emphasis at FU Weeks 12, 24, 36 and 48 (i.e. 12, 24, 36, 48 weeks after completion of all study interventions at Week 24) and without restarting NA treatment.

For the analyses of seroclearance at the time points mentioned above, participants with HBsAg seroclearance at the respective time points (and without restarting NA treatment during the interval between the time of stopping the study intervention up to the analysis time point (FU Week 12, 24, 36 and 48)) will be considered as having achieved this endpoint.

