##### **5.4.2.1.5.2. Off Treatment**

The count and proportion of participants (and associated 90% CI) who achieve HBsAg seroclearance over time during FU will be summarized by intervention arm.

The count and proportion of participants who achieve HBsAg seroclearance will be evaluated by intervention arm at each of the following off-treatment time points: 12, 24, 36 and 48 weeks, respectively, after stopping all study interventions and without restarting NA treatment. In an additional summary, these proportions will be calculated with the denominator including only those participants who have reached the off-treatment timepoint (week 12, 24, 36 or 48), and have stopped all interventions including NA and have not restarted NA prior to the timepoint of interest.

For all time points, HBsAg seroclearance will be analyzed using the observed case data. LOCF will be used for selected time points (Section 5.4.2.1.1).

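### The off-treatment endpoints at FU Weeks 24 and 48 are described as 24 and 48 weeks after all study interventions, but on-schedule NA stoppers have been off NA for only 20–22 and 44–46 weeks

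*Protocol*

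**What the plan says.** Protocol Section 3 (and the Synopsis, 1.1) sets the off-treatment objective "in those participants who met the protocol-defined NA treatment completion criteria based on the Week 24 or FU Week 2 results", that is, in participants who qualify to stop NA. The endpoints are HBsAg seroclearance and HBV DNA below LLOQ at FU Weeks 24 and 48, explained as "ie, 24 and 48 weeks after completion of all study interventions at Week 24) without re-starting NA treatment".

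SAP 1.1 carries the same text. SAP 5.4.1.1.4.2 extends it to four visits: "i.e. 12, 24, 36, 48 weeks after completion of all study interventions at Week 24) and without restarting NA treatment". SAP 5.4.1.1.10 and 5.4.2.1.10 do likewise for HBV DNA. SAP 5.4.2.1.5.2 leaves out the reference to Week 24 and speaks of "12, 24, 36 and 48 weeks, respectively, after stopping all study interventions and without restarting NA treatment".

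On dosing, Protocol 4.1 states: "All participants will receive the last dose of JNJ-3989 at Week 24". For NA, Protocol 6.5.1 says that if the criteria are met on the Week 24 results, "treatment with NA will be stopped at the next scheduled visit (ie, FU Week 2"). Participants who qualify only on FU Week 2 results "may be allowed to stop NA at FU Week 4, after consultation with the Sponsor".

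Protocol Appendix 1 counts NA as a study intervention and defines end of study intervention (EOSI) as the time of the last administration. It defines functional cure as "HBsAg seroclearance at 24-weeks after EOSI". Protocol 2.1 and 3 and SAP 5.3.1 nevertheless treat Week 24 as EOSI.

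**The concern.** The endpoint text places the completion of all interventions at Week 24. For the population the endpoints are about, that is not when all interventions end: NA continues for another 2 or 4 weeks.

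The SAP is also inconsistent with itself. Section 5.4.1.1.14 starts off-treatment time only once every intervention, NA included, has stopped, and 5.4.1.3.5 runs the off-treatment flare clock from the last intervention intake. The seroclearance and HBV DNA sections use a clock that ignores NA.

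At stake is the durability claim. NA itself holds HBV DNA near or below LLOQ (Protocol 2.3.1.2), so time since NA stop is the relevant clock for an endpoint of HBV DNA below LLOQ without restarting NA. A report that copied the endpoint wording would credit the trial with 24 and 48 weeks off treatment that on-schedule stoppers do not have.

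**Working it through.** **Inputs.** Schedule of Activities (Protocol 1.3), follow-up days: FU Week 2 = 15, Week 4 = 29, Week 12 = 85, Week 24 = 169, Week 28 = 197, Week 36 = 253, Week 48 = 337, each ± 4 days. Footnote a times follow-up visits from the Week 24 visit (follow-up day 1). NA stop is dated at the FU Week 2 or FU Week 4 visit; this is an assumption, and a last tablet on the day before would change the results by one day.

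**The plan's figures, clock at the Week 24 visit.** (169 − 1)/7 = 24.0 and (337 − 1)/7 = 48.0. The stated 24 and 48 weeks reproduce on this clock, which is time since the last JNJ-3989 dose.

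**Clock at the last intervention stopped (NA).** Weeks off = (visit day − stop day)/7.

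| Visit | NA stop at FU Week 2 | NA stop at FU Week 4 |
|---|---|---|
| FU Week 12 | (85 − 15)/7 = 10 | (85 − 29)/7 = 8 |
| FU Week 24 | (169 − 15)/7 = 22 | (169 − 29)/7 = 20 |
| FU Week 36 | (253 − 15)/7 = 34 | (253 − 29)/7 = 32 |
| FU Week 48 | (337 − 15)/7 = 46 | (337 − 29)/7 = 44 |

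The stated figures do not reproduce. The shortfall is always 2 or 4 weeks: 8% or 17% of 24 weeks (2/24, 4/24), and 17% or 33% of 12 weeks (2/12, 4/12).

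**Protocol visit windows used in full.** A stop 4 days early and a FU Week 48 visit 4 days late give (341 − 11)/7 = 47.1 weeks, or (341 − 25)/7 = 45.1 weeks for the FU Week 4 route. Neither reaches 48.

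**SAP analysis windows (Table 4).** These are wider. FU Week 24 runs to day 183, so a FU Week 2 stopper at its upper edge would be at (183 − 15)/7 = 24.0 weeks. The FU Week 48 window has no upper limit.

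**Where the stated durations would fall.** 24 weeks off NA falls at FU Week 26 or 28 (24 + 2, 24 + 4). 48 weeks falls at FU Week 50 or 52, which is study Week 74 or 76, after participation ends at Week 72. The existing FU Week 28 visit is at (197 − 15)/7 = 26 or (197 − 29)/7 = 24 weeks off NA.

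**The case against.** The best defence is that nothing is ambiguous where it counts. The endpoints name FU Weeks 24 and 48, SAP Table 4 gives the day windows, and the faulty clause itself ends at Week 24, so the intended clock is visible. For the two agents labelled investigational, at least 24 and 48 weeks have passed. NA is labelled background. No participant's response status changes, and the stopping rule is the same in every arm, so no between-arm bias is shown.

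All of that stands, and it limits the problem to the stated duration. It does not rescue the wording: the documents define NA as a study intervention, and the SAP's off-treatment definition names it expressly.

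A reader might go on to infer three stronger things that the documents do not support.

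- *That functional cure is declared 2 to 4 weeks before its definition allows.* This takes EOSI as the last NA dose. Protocol 2.1 and 3 and SAP 5.3.1 place EOSI at Week 24, and SAP 5.4.1.1.5 evaluates functional cure by named FU week. There are two competing dates to reconcile, not a failed definition.
- *That the restricted summary at Week 48 has an empty denominator.* SAP 5.4.2.1.5.2 and 5.4.2.1.10 require participants to have reached the timepoint and, separately, to have stopped everything including NA without restarting. Read by FU visit, which 5.4.2.1.10 supports, the denominator is NA stoppers who reached FU Week 48, and the summary can be produced.
- *That 48 weeks off all treatment can never be observed.* A participant who stops JNJ-3989 early may also stop NA and is followed for 48 weeks from the end of JNJ-3989 (Protocol 6.5.1), and a late visit could fall in the open-ended FU Week 48 window. Neither is the planned route, but both are exceptions.

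**Conclusion.** The description is wrong as written. For participants who meet the completion criteria and stop NA on schedule, FU Week 24 is 22 or 20 weeks, and FU Week 48 is 46 or 44 weeks, after all study interventions. With both visits inside the protocol windows the maximum at FU Week 48 is about 47 weeks.

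This rests on NA being a study intervention, on stops at the scheduled FU Week 2 or FU Week 4 visit, and on follow-up timed from the Week 24 visit; all but the exact day of the last tablet come from the documents. The effect is on the off-treatment duration the trial can claim, and on the 2-week difference between the two stop routes. Computability of the endpoints, the primary endpoint and the sample size are not affected. It merits correction before reporting as more than a clerical slip, because it changes a stated property of the main off-treatment endpoints.

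**What to change.** Keep the FU Week 12, 24, 36 and 48 visits and make these changes:

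1. In Protocol 1.1 and 3 and SAP 1.1, 5.4.1.1.4.2, 5.4.1.1.10, 5.4.2.1.5.2 and 5.4.2.1.10, replace the explanatory clause with *weeks after the Week 24 visit (last JNJ-3989 dose); about 20–22 and 44–46 weeks after NA stop at FU Weeks 24 and 48*. Do not report these results as 24 or 48 weeks off all treatment.
2. Summarise off-treatment time from each participant's actual last NA date.
3. State that the restricted denominators in SAP 5.4.2.1.5.2 and 5.4.2.1.10 are defined by FU visit, among NA stoppers who have not restarted.
4. Reconcile the Appendix 1 definition of EOSI with the use of Week 24 as EOSI, so that functional cure has one date.
5. Bring SAP Table 13 rows 45 and 46, which still refer to stopping NA at Week 24, into line with Protocol 6.5.1.

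Optionally, add seroclearance at FU Week 28 among NA stoppers (24–26 weeks off NA) as a supplementary summary. That visit is already mandatory for them, with quantitative HBsAg scheduled. It should not replace FU Week 24: the LOCF rules, the correlation table and an interim analysis are built on that visit, and FU Week 28 is optional for participants who continue NA.

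The cost is SAP wording, a clarification of the protocol endpoint text and one derived time variable. No new visits or samples are needed.
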